5.4 Physician behavior and kidney disease management

After collecting the urine sample and calculating the UACR value, the patient will feed back the test results to his/her doctor. This study will record the doctor's current diagnosis, and use the method of reviewing medical records to evaluate whether he/she provides a new diagnosis and prescription for the patient's renal function.

6 Statistical Considerations

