4.1 Study data collection plan

The PLACARD study will be a cross-sectional observational study that collect patient information only once after screening and retrace the case system after the first visit, without any follow-up. It is expected that each center will complete the screening and

enrollment of patients within one month.

During the information collection period the investigator will:

1. Sign the informed consent form: Before signing the informed consent form, the participants should be fully informed of the research purpose and how the data will be used, and the researcher should also sign the informed consent form. The investigator and the patient each keep an original signed informed consent form;

2. Patient screening form: After signing the informed consent form, it will be confirmed whether the patient meets all the inclusion criteria and not all exclusion criteria, and the screening information will be recorded in the patient screening form. In order to ensure the continuity of screening, the screening information of potential patients who failed to enroll will also be recorded in the patient screening form;

3. After the patients are enrolled, the researchers should complete the following tasks and collect relevant data:

- Demographic information: gender, date of birth, education, type of medical insurance;
- Patient history: T2DM, hypertension, hyperlipidemia, coronary heart disease, atrial fibrillation, heart failure, stroke (ischemic and hemorrhagic), transient ischemic attack (TIA), cataracts, and macular degeneration;
- History of surgical intervention: coronary intervention, coronary artery bypass grafting and coronary angiographic stenosis;
- Questionnaire: Edinburgh Intermittent Claudication Questionnaire (ECQ) ;
- Physical examination: blood pressure, heart rate, height and weight;
- Clinical assessment information: blood glucose (including HbA1c , fasting blood glucose,

two-hour postprandial blood glucose), renal function (including serum creatinine glomerular filtration rate, UACR), blood lipids (including total cholesterol, LDL cholesterol, HDL Cholesterol, triglycerides), funduscopy, and the detection frequency of the above inspections in the past year (mainly based on patient self-report);

- Whether the doctor prescribes urine routine examination for inpatients, and whether the doctor issues a new doctor's order after the outpatients report back the renal function examination;

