- Combined drug information: this prescription drug and commonly used drugs (outpatients) and medications during hospitalization (inpatients);
- Information about patient behavior: smoking history and drinking history;
- UACR value detected on the day of enrollment;
- The result of funduscopy gained on the day of enrollment.

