4.3 Research procedure

The patient recruitment consisted of two parts, 50 patients from outpatients attending the Department of Cardiology and 50 from in patients receiving treatment in the Department of Cardiology.

- In the outpatient department, a selected, representative cardiologist should be followed and eligible patients among the physician's visits would be continuously screened. It is necessary to communicate with the person in charge of the Department of Cardiology

[figure not shown]
before the start of the branch center to determine the following outpatient doctors, and plan and determine the enrollment process with the outpatient doctors in advance. On the screening day, record and follow the T2DM patients encountered by the doctor during the consultation process, communicate with the patient for informed consent, screen according to the inclusion criteria, and generate a study number for those who meet the enrollment criteria (see flow chart 1).

- In the ward selected by the inpatient department of the Department of Cardiology, the clinical coordinator conducts a preliminary examination of all inpatients in the ward through the hospital medical record system, records the patient with T2DM, and communicates with the patient for informed consent, according to the inclusion and exclusion criteria, screening is carried out, and those who meet the inclusion conditions are enrolled and a research number is generated (see flow chart 2).

[figure not shown]
A face-to-face questionnaire should be conducted on the enrolled patients and baseline information such as, medical history, clinical assessment information, medication information, and living habits should be collected; and physical examination, UACR tests and funduscopy were performed on the patients. For outpatients, it is also necessary to query all the medical records of the enrolled patients on the day after the day of enrollment to supplement any missing information.

To evaluate the doctor's attention to chronic kidney disease, this study mainly reviewed the doctor's order to observe whether the doctor prescribes the UACR checklist for patients with T2DM to monitor the renal function of the patients. If the doctor has issued a UACR test for the patient, record the inspection value; if the doctor has not prescribed the test, use the

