UACR measurement equipment provided in this study to obtain the results. When all the research-related information of the enrolled patients is collected, and the UACR results are obtained and fed back to the doctors, the data collection process is deemed to be over. In addition, after the doctor obtains the results of the UACR examination, whether to revise the doctor's order based on the detected nephropathy is also one of the ways to measure the doctor's awareness of the identification and management of the nephropathy of diabetic patients in the cardiology department.

Flowchart 1, Outpatient enrollment process

Flowchart 2, Inpatient enrollment process

5 Research evaluation

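### The post-result indicator of doctors' awareness registers only change after the UACR is fed back, so nephropathy that was already diagnosed can look like inaction

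*Protocol*

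**What the plan says.** The protocol describes the doctor's reaction to the UACR result in three places:

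- **Section 5.4:** after the result reaches the doctor, the medical record is reviewed to "evaluate whether he/she provides a new diagnosis and prescription for the patient's renal function". The same sentence opens with "This study will record the doctor's current diagnosis", without saying whether that diagnosis predates the result.
- **Section 4.3:** "whether to revise the doctor's order based on the detected nephropathy is also one of the ways to measure the doctor's awareness" of identifying and managing nephropathy in diabetic patients.
- **Section 4.1:** a data item for outpatients, "whether the doctor issues a new doctor's order after the outpatients report back the renal function examination".

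It also names indicators that need no reaction to the result. Section 4.3 says that to evaluate attention to CKD "this study mainly reviewed the doctor's order to observe whether the doctor prescribes the UACR checklist for patients with T2DM", and section 4.1 has an inpatient item, "Whether the doctor prescribes urine routine examination for inpatients".

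The history list in section 4.1 begins "Patient history: T2DM, hypertension, hyperlipidemia, coronary heart disease, atrial fibrillation, heart failure, stroke" and runs on to macular degeneration. It contains no CKD or diabetic nephropathy item. Current and commonly used drugs are collected. The endpoints in section 6 include no score of physician awareness.

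**The concern.** The stated target is recognition and management of nephropathy. What is recorded after the result is whether something changed. The two agree for a patient whose kidney disease was unknown. They part for a patient whose nephropathy was diagnosed earlier: the doctor recognised the disease, yet may show no new diagnosis, prescription or order. Such patients can enrol, because section 3.7.2 excludes dialysis and confirmed primary glomerular disease but does not name diabetic kidney disease.

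Other things equal, the indicator therefore falls as prior recognition rises. A low value could mean that results were ignored or that the disease was already known, and nothing fixed in the protocol tells the two apart. The base is also unsettled: only section 4.3 ties the indicator to detected nephropathy, while sections 4.1 and 5.4 do not say whether patients with a normal UACR are counted.

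**Working it through.** **Plan figures.** No figure in the protocol tests this point. The only usable planning inputs are in section 6.6: 3,000 patients and 50% prevalence, hence 0.50 × 3,000 = 1,500 albuminuric patients. The stated precision reproduces: 50% ± 1.96 × √(0.25/3,000) gives 48.21% to 51.79%, width 3.58%, against the stated 48.2%, 51.8% and 3.6%. It has no bearing on the indicator.

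**Three patients under the wording of 5.4, 4.3 and 4.1**

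| Patient | What the doctor did | New action recorded? | Nephropathy recognised? |
|---|---|---|---|
| UACR 120 mg/g, no renal diagnosis | Adds diagnosis and prescription | Yes | Yes |
| UACR 120 mg/g, renal diagnosis already in the record | Sees no need for change | No | Yes |
| UACR 10 mg/g | Nothing to act on | No | Does not apply |

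The second patient has no category in any of the three sections. The third is outside the base in 4.3 and undetermined in 4.1 and 5.4.

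**Size.** Among albuminuric patients let

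- k = share with nephropathy already recognised (not given; assumed 5%, 20%, 40%),
- r = share of the rest who receive a new diagnosis, prescription or order (not given; 50% for illustration),
- s = share of the already recognised who also show some new action (taken as 0).

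Then

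- indicator = (1 − k)r + ks
- recognition, counting prior and new = k + (1 − k)r
- gap = k(1 − s), which equals k when s = 0, whatever r is.

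| k | Indicator, (1 − k) × 0.5 | Recognition, k + (1 − k) × 0.5 | Gap | Patients of 1,500 |
|---|---|---|---|---|
| 5% | 47.5% | 52.5% | 5 points | 75 |
| 20% | 40% | 60% | 20 points | 300 |
| 40% | 30% | 70% | 40 points | 600 |

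With s above 0 the gap shrinks, so k is its upper limit.

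**Is the range of k plausible?** Section 1.3 cites 23% of Swedish CKD patients with the diagnosis in their electronic record, and patient awareness from 5.4% (mild to moderate decline) to 41.8% (severe decline). These are other populations, and the awareness figures concern patients, not doctors. They only show that 5% to 40% is not outlandish. At 23% the gap would be 23 points, 0.23 × 1,500 = 345 patients.

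**Can planned data separate the groups?** Not reliably. The history list lacks a renal item, and the current diagnosis in 5.4 has no stated timing relative to feedback. Drugs do not settle it: section 1.1 lists RAAS inhibitors and SGLT-2 inhibitors as first-line treatment for T2DM generally, so prior use does not show that nephropathy was recognised.

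**The case against.** The strongest reply is that the protocol describes data collection and sets no scoring rule. Section 4.3 makes the doctor's own UACR order the main indicator of attention, and a doctor who knows of the disease and monitors it does well there. It presents order revision as one further indicator. Section 5.4 records the current diagnosis, a diagnosis can be called new only against what was there before, and section 5.2 checks records for consistency with disease and medication history. Tabulation may be settled in an SAP that is not shown.

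Much of this stands, and it rules out three stronger readings:

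- *Awareness is judged only by new action.* Sections 4.1 and 4.3 name other indicators.
- *Already treated patients are counted as not recognised.* No section states such a score or a denominator. Sections 6.1 and 6.2 (non-missing data, all enrolled patients with UACR) could suggest an all-patient base, but neither is applied to this indicator.
- *Hospital levels with better prior recognition will rank lower.* The hospital-level endpoints concern management of risk factors and complications and do not mention new orders. A reversal also needs assumed differences in prior recognition.

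What the reply does not remove is the capture problem. An SAP can define classes, but it cannot supply the timing of a renal diagnosis if the CRF does not hold it. Data are collected once, without follow-up.

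**Conclusion.** The point holds for the post-result indicator alone. As described in 4.3, 5.4 and 4.1 it measures change after feedback, while 4.3 presents it as a measure of awareness. If it is read as awareness over all albuminuric patients, it understates recognition by up to the share already recognised: 5 to 40 percentage points for an assumed 5% to 40%, on the assumption that none of those patients shows any new action. The true share is not in the protocol, so the direction of the bias is firmer than its size.

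The consequences are limited. The indicator is one of several, is not a listed endpoint, and does not touch the primary prevalence estimate. It still merits correction, because without the timing of the renal diagnosis a low value cannot be interpreted.

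**What to change.** 1. Add one CRF field: was a renal diagnosis (CKD or diabetic nephropathy) in the record before the UACR result was fed back?
2. Align sections 4.1, 4.3 and 5.4 on one definition, restricted to patients with UACR of at least 30 mg/g, and state whether it covers inpatients, since the new-order item in 4.1 names outpatients only.
3. Report three classes separately: (1) renal diagnosis recorded before feedback; (2) no prior diagnosis, with a new diagnosis, prescription or revised order after feedback; (3) neither.
4. Report response to the result as (2)/((2) + (3)). Report prior recognition, class (1), on its own and not pooled with class (2), which was prompted by the study's own feedback.
5. Do not take prior use of RAAS inhibitors or SGLT-2 inhibitors alone as recognition.

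The cost is one field and wording in three sections, with no change to patient care. The response measure has a smaller base: 1,500 × (1 − k), or 1,425 to 900 patients for k from 5% to 40%, if both settings are included. At 900 and a 50% response, the simple-random-sampling 95% half-width is 1.96 × √(0.25/900) = 3.3 points, against 2.5 at 1,500.

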6.1 General considerations

This study will be performed using SAS 9.4 statistical software. Descriptive statistics are calculated and reported, including number of observations, means, standard deviations, medians, and interquartile ranges for continuous variables, and frequencies and percentages for categorical variables. Percentages will be calculated based on non-missing data unless otherwise specified. The data will be checked for bias and outliers. Conversion will be done as needed. Missing data will be assumed to be missing at random or completely at random, and no imputation will be applied except in special circumstances.

6.2 Definition of analysis set

The full analysis set will include all enrolled participants with UACR data.

6.3 Outcome Analysis

6.3.1 Main endpoint

The primary endpoint of this study will be the prevalence of albuminuria (UACR \geq 30 mg/g) in patients with type 2 diabetes presented to the Department of Cardiology , and the prevalence of albuminuria and other demographic characteristics will be assessed by descriptive abstracts. In summary, the relationship between the stage of renal impairment/disease (A1-A3 or GFR classification) and relevant covariates was analyzed by logistic regression model. Crude ORs and multivariate-adjusted ORs will be reported, including covariates including:

Age group (18-39 years old, 40-59 years old, 60-69 years old, \geq 70 years old); gender; BMI group (18.5, 23.9, 27.9, 28), blood pressure, blood lipid (LDL, HDL, TG), living habits (smoking, drinking); sub-research centers, nephrotoxic drugs being used, disease history.

Prevalence will be analyzed grouped by stratification factors, gender and age, geographic

region (East, South, Central, North, Northwest and Southwest), etc.

6.4.2 Secondary endpoints

(1) Albuminuria level in patients with T2DM in the Department of Cardiology (microalbuminuria means UACR value >30 and <300 mg/g; macroalbuminuria means UACR value ≥ 300 mg/g);

(2) The prevalence and level of albuminuria in different types of cardiovascular diseases in the Department of Cardiovascular Medicine (microalbuminuria refers to UACR values >30 and <300 mg/g ; macroalbuminuria refers to UACR values ≥ 300 mg/g);

(3) Different treatment patterns for patients with CKD and patients without CKD;

(4) Assessing the current status of disease-related risk factor management in patients with T2DM attending cardiovascular medicine departments at different levels of hospitals;

(5) Evaluating the management of complications in patients with T2DM in different levels of hospitals.

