Prevalence of Albuminuria in patients with Cardiovascular
Disease and
Type 2 Diabetes mellitus in China: a national cross-sectional
study PLACARD

Research Protocol

<< Version 3.1 , October 26, 2023 >>

main researcher: [name]
Team leader unit: Beijing Anzhen Hospital
Sponsor: Heart Health Research Center
Financial Bayer HealthCare Co., Ltd.
Sponsor:

Principal Investigator Statement

I have read the following research protocol:

Research protocol title: Prevalence of Albuminuria in patients with Cardiovascular Disease and Type 2 Diabetes mellitus in China: a national cross-sectional

Version and date: Version 3.1, October 26, 2023

I have read the study protocol and all study documents and agree that they contain all necessary details to conduct the study. I will follow the protocol and complete the research within the allotted time. I will provide a copy of the study protocol and all relevant information to all principals and sub-centre investigators assisting with the conduct of the study. I will discuss the material with them to ensure they fully understand the mission and conduct of the study.

Investigator's signature:

main researcher:

[name] _____
date signature

Research Protocol Overview

Study title	Prevalence of Albuminuria in patients with Cardiovascular Disease and Type 2 Diabetes mellitus in China: a national cross-sectional
Research objectives	
Primary Objective
 
To assess the prevalence of albuminuria in patients who are combined with type 2 diabetes mellitus and different cardiovascular diseases in inpatient and outpatient cardiology departments of secondary and tertiary hospitals in China.
 
Secondary Objectives
 
(1) To evaluate the levels of microalbuminuria and macroalbuminuria of patients with type 2 diabetes mellitus (T2DM) in inpatients and outpatients cardiology departments;
 
(2) To evaluate the prevalence of microalbuminuria and macroalbuminuria in patients with T2DM complicated with different cardiovascular diseases;
 
(3) To evaluate the related influence factors of albuminuria and the treatment patterns of CKD patients and non-CKD patients in cardiology departments;
 
(4) To evaluate the management of risk factors and complications in cardiovascular departments of patients with T2DM complicated with microalbuminuria and macroalbuminuria in different levels of hospitals.
 
Exploratory Objective

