2.2 Secondary objectives

(1) To evaluate the levels of microalbuminuria and macroalbuminuria of patients with type 2 diabetes mellitus (T2DM) in inpatients and outpatients cardiology departments;

(2) To evaluate the prevalence of microalbuminuria and macroalbuminuria in patients with T2DM complicated with different cardiovascular diseases;

(3) To evaluate the related influence factors of albuminuria and the treatment patterns of CKD patients and non-CKD patients in cardiology departments;

(4) To evaluate the management of risk factors and complications in cardiovascular

departments of patients with T2DM complicated with microalbuminuria and macroalbuminuria in different levels of hospitals.

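### Secondary objective 4 is about T2DM patients with micro- or macroalbuminuria, but the endpoints that serve it (4 and 5) cover all T2DM patients and are nowhere split by albuminuria

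*Protocol*

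**What the plan says.** Objective 4 has the same population in both places where it appears. The Research Protocol Overview speaks of "management of risk factors and complications in cardiovascular departments of patients with T2DM complicated with microalbuminuria and macroalbuminuria in different levels of hospitals", and section 2.2 repeats the restriction: "departments of patients with T2DM complicated with microalbuminuria and macroalbuminuria in different levels of hospitals".

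Section 6.4.2 divides this objective into two endpoints. Endpoint (4) covers risk factors: "Assessing the current status of disease-related risk factor management in patients with T2DM attending cardiovascular medicine departments at different levels of hospitals". Endpoint (5) covers complications: "Evaluating the management of complications in patients with T2DM in different levels of hospitals". Both keep the comparison across hospital levels. Neither mentions albuminuria.

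Only one analysis set is defined, in section 6.2: "The full analysis set will include all enrolled participants with UACR data". UACR is part of the data collected on every enrolled patient (section 4.1: "UACR value detected on the day of enrollment").

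**The concern.** An objective and its endpoint should describe the same patients. Here the objective concerns patients with albuminuria and the endpoints concern everyone with T2DM. An analyst who follows section 6.4.2 to the letter would tabulate management over the whole analysis set by hospital level, and would have no instruction to produce the figure that objective 4 asks for. If the split is first made once data are in hand, it is a post hoc choice and not a stated endpoint.

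The comparison between hospital levels is exposed as well. If albuminuria is more common at one level than at the other, all-patient figures for the two levels rest on different mixes of patients with and without albuminuria.

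**Working it through.** **1. Does any section close the gap?**

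| Place in the protocol | What it covers | Splits endpoints 4 and 5 by albuminuria? |
|---|---|---|
| Overview and 2.2, objective 4 | T2DM with micro- or macroalbuminuria, by hospital level | This is the target |
| 6.4.2, endpoint (4) | T2DM, risk factor management, by hospital level | No |
| 6.4.2, endpoint (5) | T2DM, complication management, by hospital level | No |
| 6.4.2, endpoint (3) | CKD against non-CKD, treatment patterns | No; serves objective 3 |
| 6.2 | Everyone enrolled with a UACR | No |
| 6.3.1, grouping by sex, age, region and so on | Prevalence | No |
| 6.5.2, stratification by centre, sex, age, concomitant medication and unnamed further factors | Control of confounding | Albuminuria is not named |

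Nothing closes it.

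**2. Inputs from section 6.6.** N = 3,000; planning prevalence 50%; 18 tertiary and 12 secondary centres at 100 patients each, so 1,800 and 1,200 patients. The upper prevalence of 59.9% is the mainland China figure cited there. The lower value of 30% is an assumption. All enrolled patients are taken to have a UACR.

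**3. The plan's own figure.** The half-width is 1.96 × √(0.5 × 0.5 / 3,000) = 1.79 points, which gives 48.2% to 51.8% and a width of 3.6 points. This matches section 6.6. That figure concerns overall prevalence and says nothing about objective 4.

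**4. Share of endpoints 4 and 5 outside the objective's population, 1 − p.**

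- p = 30%: 70%, or 2,100 of 3,000
- p = 50%: 50%, or 1,500 of 3,000
- p = 59.9%: about 40%, or 1,203 of 3,000

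**5. Gap between the two quantities.** Let a be the management rate in patients with albuminuria and b the rate in those without. The endpoint as written estimates p·a + (1 − p)·b, and the objective asks for a. The gap is

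p·a + (1 − p)·b − a = (1 − p)(b − a).

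The protocol gives neither a nor b. Purely for scale, a 20-point difference in either direction (assumption) gives a gap of 14 points at p = 30%, 10 points at 50% and 8 points at 59.9%. With a = 60% and b = 40% at p = 50%, the all-patient figure is 50%, too low for the objective by 10 points. With a = 30% and b = 50% it is 40%, too high by 10 points. If a = b the gap is zero.

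**6. Precision if the endpoints are reported in the albuminuria group, by hospital level.** The half-width is 1.96 × √(0.25 / n) at a management proportion of 50%.

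| Prevalence | Tertiary n | Half-width (points) | Secondary n | Half-width (points) |
|---|---|---|---|---|
| 30% (assumed) | 540 | 4.2 | 360 | 5.2 |
| 50% | 900 | 3.3 | 600 | 4.0 |
| 59.9% | 1,078 | 3.0 | 719 | 3.7 |

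Pooled over levels at 50% prevalence, n = 1,500 and the half-width is 2.5 points. The by-level figures are the relevant ones, because the objective is by hospital level. None of these allows for clustering by centre, which would normally widen them.

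**The case against.** The best defence is that section 6.4.2 is a list of short endpoint labels and not a specification of tables. It shortens populations elsewhere: the primary objective names T2DM with different cardiovascular diseases, while the primary endpoint in section 6.3.1 mentions only T2DM patients seen in cardiology. Nothing forbids a breakdown by albuminuria, every patient in the analysis set has a UACR by definition, and subgroup tables for a descriptive secondary endpoint are commonly left to the SAP. The endpoints are descriptive, with no pre-defined hypothesis tests (section 6.6), and the primary result is untouched.

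Part of this stands. A reader might infer that the study cannot answer objective 4, or will never report it. The documents do not support that: the data needed are collected, and an SAP that is not shown may contain the split. What does not stand is the appeal to the SAP as a full answer. The protocol names two different populations for one question, and an SAP that follows section 6.4.2 faithfully carries the mismatch forward.

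It is also fair to say that the protocol does not show which of the two populations was intended. Widening objective 4 to all T2DM patients would make the text consistent too, though it would give up a question that is stated identically in two places.

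**Conclusion.** The point holds as an internal mismatch between objective and endpoints. About half of the patients behind endpoints 4 and 5 fall outside objective 4 at the planning prevalence, and 70% to 40% do so over prevalences of 30% (assumed) to 59.9%. The resulting gap is (1 − prevalence) times the difference in management rates between patients with and without albuminuria, and its size and sign are unknown.

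A reader might go further and infer that the all-patient figure will look too favourable and conceal under-management of patients with albuminuria. The documents do not support that. They give no management rates, objective 4 sets out to evaluate management without presuming that it is poor, and the gap could equally run the other way.

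This is a wording and target-population error in a secondary, descriptive part of the study. It should be corrected, but it is not a design failure.

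**What to change.** Reword endpoints (4) and (5) in section 6.4.2 so that both are reported by albuminuria category and hospital level, and state that the group with UACR at or above 30 mg/g answers objective 4. The all-T2DM figure can stay alongside.

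Use one set of boundaries: below 30, 30 to below 300, and 300 mg/g or above. At present section 6.3.1 counts a UACR of exactly 30 as albuminuria, while section 6.4.2 starts microalbuminuria strictly above 30. Micro plus macro therefore does not quite equal albuminuria as the primary endpoint defines it. Aligning the lower bound with the primary endpoint removes this. Showing the two albuminuria categories separately also lets the reader see whether their ratio differs between hospital levels.

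The cost is the rewording, one more split in two tables, and the wider by-level intervals shown above. No new data are needed.
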